9.2.1. Inclusion Criteria

Patients must meet all of the following inclusion criteria to be eligible for inclusion in the study:

1. Index date: First observed prescription claim or medical claim for elranatamab in the dataset (14 August 2023 to the end of data)
2. Age 18 or older on index date

3. Diagnosis of RRMM (defined as MM) any time prior to index date
4. At least 180 days of continuous closed-claims medical and pharmacy enrollment prior to index (inclusive)

For the exploratory cohort of patients receiving teclistamab, patients will be required to meet the same inclusion criteria as those receiving elranatamab. The only difference is that patients will index on their first teclistamab claim within the same time window (14 August 2023 to the end of data).

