9.3. Variables

Table 1 includes definitions and assessment periods for all study variables that will be used as eligibility criteria. The full code list can be found in ANNEX 2. ADDITIONAL INFORMATION.

Table 1. Variables Used to Determine Eligibility

Variable	Operational Definition	Role	Assessment Period
Elranatamab	Prescription claim or medical claim with a National Drug Code (NDC), Healthcare Common Procedure Coding System (HCPCS), ICD-10 code or generic name in the IP, non-IP or pharmacy setting for elranatamab	Inclusion	Index event
Teclistamab	Prescription claim or medical claim with an NDC, HCPCS, ICD-10 code or generic name in the IP, non-IP or pharmacy setting for teclistamab	Exclusion	All available data to index date

Variable	Operational Definition	Role	Assessment Period
Age	Age is greater than or equal to 18 years and is not missing	Inclusion	Index date
MM diagnosis	Medical claim in the IP or non-IP setting with an ICD-10 code for MM	Inclusion	All available data to index date
Observability	Closed-claims medical and pharmacy enrollment	Inclusion	180 days prior to index date to index date (inclusive)

Table 2 includes definitions and assessment periods for all study variables that will be used as baseline and treatment characteristics. The full code list can be found in ANNEX 2.
 ADDITIONAL INFORMATION. If applicable, the frequency and percentage of patients with missing data for each variable will be described.

Table 2. Variables Used to Determine Baseline and Treatment Characteristics

Objective	Variable	Definition	Assessment Period(s)
1	Age	Age in years (continuous)	Index date
1	Sex	Categorical sex Male Female	Index date
1	Race/Ethnicity	Categorical race and ethnicity Caucasian African American Asian or Pacific Islander Hispanic or Latino Other	Start of data availability to index date

Objective	Variable	Definition	Assessment Period(s)
		Unknown	
1	Region	Categorical region, assessed as the most recent value from index date Northeast Midwest West South	Start of data to index date
	Insurance type	Categorical insurance type, assessed as the most recent value to index date Commercial Medicaid Medicare Other Unknown	180 days prior to index date to index date
1	Location (Zip code)	Categorical zip code assessed as the most recent value from index date. The full categories will be reported during implementation.	Index date
1	Care setting	Categorical care setting for elranatamab or teclistamab administration IP Non-IP Pharmacy	Index date

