2	Reported vial size	
Reported vial size in the following categories (categorical):
 
 • Unknown vial – IP dose • 44 milligram (mg)/1.1 milliliter (mL) • 76mg/1.9mL • Missing dose/unknown dose 
For the exploratory cohort of teclistamab patients the reported vial size (categorical):
 
 • Unknown vial – IP dose • 30mg/3mL • 153mg/7mL 
Missing dose/unknown dose
	
Index date to the end of follow-up
 
Index date
 
Step-Up Dosing Period
 
Maintenance Periods
 
See Section 9.7.2 for more information on the assessment periods and censoring criteria

2	Patients with 2 or more administrations	Proportion of patients with 2 or more administrations of elranatamab during the assessment period	
Index date to the end of follow-up
 
Step-Up Dosing Period
 
Maintenance Periods
 
See Section 9.7.2 for more information on the assessment periods and censoring criteria

2	Average time between elranatamab claims	Sum of the days between claims for the index drug (continuous) divided by the total number of administrations -1 reported among patients with 2 or more administrations	Index date to the end of follow-up Step-Up Dosing Period Maintenance Periods See Section 9.7.2 for more information on the assessment periods and censoring criteria
2	Number of elranatamab claims	Total number of IP, non-IP, and pharmacy claims of the index drug during the time period based on vial size (continuous)	Index date to the end of follow-up Step-Up Dosing Period Maintenance Periods See Section 9.7.2 for more information on the assessment periods and censoring criteria
3	RAI	The ratio of the actual administrations received divided by the expected number of administrations (continuous) See Section 9.7.3 for more details.	Index date to the last administration of the index drug Step-Up Dosing Period Maintenance Periods See Section 9.7.2 for more information on the assessment periods and Section 9.7.3 for censoring criteria
3	Duration on treatment	Time in days between first and last treatment administration for the index treatment (continuous)	Index date to the end of follow-up See Section 9.7.2 for censoring criteria

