		PJP Hepatitis C Hepatitis B Other infectious hepatitis Helicobacter pylori Candida esophagitis Urinary tract infection	
Effectiveness			
Exploratory Obj 2	OS	Time (in months) from index date until date of death (continuous)	Index date until censor See Section 9.7.7 for censoring criteria
Exploratory Obj 2	TTNT/D	Time (in months) from index date until the date of the next treatment (CAR-T, BsABs, bendamustine or belantamab) or death (continuous)	Index date until censor See Section 9.7.7 for censoring criteria

1. Variable will be measured as incident and prevalent. Incident cases have 30-day washout period applied
2. Variable will be measured as incident and prevalent. Incident cases have 60-day washout period applied
3. Variable will be measured as incident and prevalent. Incident cases have 14-day washout period applied

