9.7.2. Treatment Exposure Outcomes

Treatment exposure outcomes include RAI and time between administrations. The assessment periods shown in Table 4 are based on the elranatamab label instructions and will be used to measure treatment and dosing-related outcomes for patients receiving elranatamab.¹⁸ These periods are also provided in Figure 2.

[figure not shown]
Table 4. Dosing Schedule and Expected Administrations and Vial Size of Elranatamab

Dosing Schedule	Time Period	Expected Administrations	Vial Size

[figure not shown]
Step-Up	Index date - Day 8	3 during Step-Up	44mg/1.1mL
Maintenance Period 1	Day 9 - Day 168	1 per week	76mg/1.9mL
Maintenance Period 2	Day 169 – Censor	1 every two weeks	76mg/1.9mL

Figure 2. Dosing Schedule for Elranatamab and Teclistamab

Elranatamab label instructions

Teclistamab label instructions

The assessment periods shown in Table 5 are based on the teclistamab label instructions and will be used to measure treatment and dosing-related outcomes for patients receiving teclistamab.¹⁹ These periods are also provided in Figure 2.

Table 5. Dosing Schedule and Expected Administrations and Vial Size of Teclistamab

Dosing Schedule	Time Period	Expected Administrations	Vial Size
Step-Up	Index date - Day 7	3	30 mg/3mL
Maintenance Period	Day 8 - Censor	1 per week	153 mg/1.7mL

Dosing outcomes (reported vial size, average time between claims, and frequency of claims) will be assessed during the above time periods regardless of whether the number of administrations during the period matches the number indicated on the label instructions. Duration on treatment will be measured from the first administration to the last administration of the index drug.

Patients will be censored at the earliest of death, next treatment (CAR-T, BsABs, bendamustine, or belantamab), the end of observability, or the latest data at the time of the specified analysis.

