9.7.5. Healthcare Resource Utilization and Cost

All-cause HCRU and MM-related HCRU (ie, HCRU with a diagnosis code or treatment for MM) will be measured as the total number of IP, OP, ED, and pharmacy claims that occurred over the follow-up period. Medical claims will only be counted once per day to estimate

visits, pharmacy claims will count all claims including multiple on the same day. Additionally, the total length of IP stays will be reported among patients with at least one IP visit. Given the recency of the study period, costs will not be adjusted for inflation. As the number of HCRU claims will vary by patient follow up time, results will also be reported as PPPM.

HCRU and associated costs will be measured across four different time periods. The first time period will be from 180 days prior to index date to one day prior to the index date, the second time period will be the index date until last recorded dose, the third time period will be during the step-up dosing period, the fourth time period will be the index date until discontinuation with an allowable 8-week gap of the index drug.

Patients will be censored at the earliest of death, next treatment (CAR-T, BsABs, bendamustine or belantamab), the end of continuous closed-claim coverage, or the latest data at the time of the specified analysis.

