ANNEX 2. ADDITIONAL INFORMATION

Variable	Role	Data Source(s)	Codes	Source
Elranatamab	Inclusion criteria	Claims data	HCPCS: C9165, J1323 NDC: 00069449401, 00069449402, 00069252201, 00069252202 ICD-10 Procedure code: XW013L9 Generic name: Elranatamab	ELREXFIO Outpatient Billing (2024) ELREXFIO Inpatient Billing (2024)
Teclistamab	Inclusion criteria (Exploratory cohort)	Claims data	HCPCS (Mapped via SEER using generic name): J9380, C9148 NDC: 57894044901, 57894045001 ICD-10 Procedure code: XW01348 Generic name: Teclistamab	Janssen Biotech (2023) SEER (2024)
Multiple Myeloma	Inclusion criteria, Outcome - HCRU	Claims data	C90.0x	ELREXFIO Outpatient Billing (2024)
Age	Inclusion criteria, Baseline characteristic - Demographic	Claims data	N/A	N/A
Sex	Baseline characteristic - Demographic	Claims data	N/A	N/A
Race/Ethnicity	Baseline characteristic - Demographic	Claims data	N/A	N/A

PFIZER CONFIDENTIAL

Redacted

Insurance type	Baseline characteristic - Demographic	Claims data	N/A	
Care setting	Baseline characteristic - Clinical	Claims data	See rows below: "Inpatient," "Outpatient," and "Emergency Department"	N/A
Hematopoietic stem cell transplantation	Baseline characteristic - Treatments	Claims data	
CPT: 38240, 38241, 38242, 38243
 
ICD-10 Diagnosis: T86.0, T86.00, T86.01, T86.02, T86.03, T86.09, T86.5, Z48.290, Z94.81
 
ICD-10 Procedure: 30240Y0, 30243Y0, 30250Y0, 30253Y0, 30260Y0, 30263Y0, 30230Y1, 30233Y1, 30240Y1, 30243Y1, 30230Y2, 30233Y2, 30240Y2, 30243Y2, 30230Y3, 30233Y3, 30240Y3, 30243Y3, 30230Y4, 30233Y4, 30240Y4, 30243Y4, 30253Y1, 30260Y1, 30263Y1, 30233X0, 30233G0, 30233G1, 30233G2, 30233G3, 30233X1, 30233X2, 30233X3, 30233X4, 30233Y0, 30243X0, 30243G0, 30243G1, 30243G2, 30243G3, 30243X1, 30243X2, 30243X3, 30243X4, 0243Y4, 30283X0, 30283G0, 30283G1, 30283G2, 30283G3, 30283X1, 30283X2, 30283X3, 30283X4, 30283Y1, 30283Y2, 30283Y3, 30283Y4
	
Chaudhry et al. (2022)
 
LeMaistre et al. (2013)

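### A patient whose first observed claim is for a maintenance-size vial is still analysed as starting step-up, and no rule flags or handles this

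*Protocol*

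**What the plan says.** Protocol section 9.2.1 makes the index date the "First observed prescription claim or medical claim for elranatamab in the dataset (14 August 2023 to the end of data"). The teclistamab cohort uses the same rule with its own drug. Table 1 in section 9.3 recognises the drug by NDC, HCPCS, "ICD-10 code or generic name in the IP, non-IP or pharmacy setting for elranatamab", and Annex 2 includes the inpatient entry "ICD-10 Procedure code: XW013L9".

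Section 9.7.2 counts its periods from index. In Table 4, step-up runs from index to Day 8, with "3 during Step-Up" expected and the 44 mg vial assigned; maintenance uses the 76 mg vial. In Table 5, step-up runs from index to Day 7 with 3 expected administrations and the 30 mg vial, followed by the 153 mg vial. Vial size, time between claims and claim frequency are assessed in these periods "regardless of whether the number of administrations during the period matches the number indicated on the label instructions".

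Other outcomes use the same anchor:
- Table 3 assesses premedication in the step-up period.
- Section 9.7.5 states that "the third time period will be during the step-up dosing period", and its baseline period runs from day -180 to day -1.
- Table 3 and section 9.7.6 count CRS and ICANS from index. For incidence, the Table 3 footnote reads "Incident cases have 30-day washout period applied".

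Table 3 also tabulates vial size on the index date, with a category "Unknown vial – IP dose" and another for missing or unknown dose. Table 2 tabulates care setting at index. No rule uses either variable to check that the index claim is a step-up dose.

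**The concern.** The step-up windows mean what their name says only if the earliest claim seen is the first dose given. Nothing in sections 9.2.1 or 9.7.2 requires that, although Tables 4 and 5 assign different vials to step-up and maintenance and the vial at index is already collected.

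Primary Objective 2 (administration), primary Objective 3 (resource use and cost, including the step-up period) and the CRS and ICANS estimates all depend on this anchor. A mis-indexed patient contributes a step-up record that was not observed and an apparently event-free early course. The limitations in section 9.9 do not mention unobserved initial doses.

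**Working it through.** The protocol states no figure for the share of patients affected, so there is nothing to reproduce. The check follows one mis-indexed patient through the definitions and then gives an illustrative size.

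**Tracing the definitions.** Suppose the early doses left no recognisable claim and the earliest claim seen is a weekly maintenance dose.

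1. *Step-up RAI* (section 9.7.3: administrations received / administrations expected). Counting index as Day 1, weekly doses fall on Days 1, 8, 15 and so on. Elranatamab: Days 1 and 8 are inside the window, so RAI = 2/3 = 0.67. Teclistamab: only Day 1 is inside a window ending on Day 7, so RAI = 1/3 = 0.33. The text of 9.7.2 does not state the day numbering. If index were Day 0, doses on Days 0 and 7 would give 2/3 in both cohorts. In either case the ratio says nothing about the real step-up.
2. *Premedication and step-up resource use.* Both are measured around maintenance doses.
3. *Admission before the false index.* It falls in day -180 to day -1, so it is added to baseline use and cost and is missing from the step-up and on-treatment periods.
4. *CRS or ICANS before the false index.* It is outside the window that starts at index, so it is missing from the numerator. Both formulas in section 9.7.6 divide by the whole cohort, so the patient remains in the denominator.

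**Illustrative size for CRS.**

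Inputs:
- p = 57.7%, the phase 2 trial's CRS rate quoted in section 7, taken here as the true rate.
- m = share of patients mis-indexed, assumed at 5%, 10% and 20%.
- N = 56 patients with an elranatamab claim (section 9.5).
- All CRS in affected patients precedes the false index, and CRS risk is the same in affected and unaffected patients.

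Formula: observed CRS = p × (1 − m).

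| m | Patients of 56 | Observed CRS | Shortfall (points) |
|---|---|---|---|
| 5% | 2.8 | 57.7 × 0.95 = 54.8% | 2.9 |
| 10% | 5.6 | 57.7 × 0.90 = 51.9% | 5.8 |
| 20% | 11.2 | 57.7 × 0.80 = 46.2% | 11.5 |

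The sentence above the incidence formula in 9.7.6 can be read as removing patients with a prior event from the analysis. If they were removed from the denominator as well, and the CRS fell within the 30-day washout, incidence would be p(1 − m) / (1 − mp):
- m = 5%: 0.548 / 0.971 = 56.4%
- m = 10%: 0.519 / 0.942 = 55.1%
- m = 20%: 0.462 / 0.885 = 52.2%

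The shortfall is then smaller but does not disappear.

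For scale, 32 events in 56 patients has an exact 95% interval of 43.2% to 70.3%. At this size, a 5.8-point shortfall is well inside sampling error. Unlike sampling error, it does not shrink as the quarterly refreshes add patients.

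**The case against.** The strongest reply is that the premise is not in the protocol. Inpatient claims are searched by several routes, including a procedure code, and the category "Unknown vial – IP dose" describes inpatient doses that were seen but lack vial detail. An unknown vial is not an unseen dose. This stands. A reader might infer that inpatient step-up is often missing from these data, but the documents do not show it, and the values of m above are assumptions. The 57.7% is also a trial rate; section 9.9 warns that less severe events may not be captured in claims.

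Several further points stand:
- A reader might infer a bias in one direction across Objectives 2 and 3. That is not shown: baseline use rises while step-up use falls, and a false RAI may lie above or below the true one.
- CRS and ICANS are not baseline variables in Table 2. They are lost because they precede index, not because they are reported at baseline.
- The washout adds little. A patient whose only CRS precedes index has no later event to count.
- No formal comparison between cohorts is planned (section 9.7), so an artificial difference between drugs would not feed a test.
- Re-dating index to an earlier admission with a myeloma code would assign exposure without drug evidence. In a cohort where every patient has myeloma, such an admission may have another cause.

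It can also be said that tabulating vial size at index will expose the problem, and that flags belong in a statistical analysis plan. The table would show a count, but the affected patients would remain in every step-up and CRS/ICANS denominator. A separate plan could add a flag. However, this protocol itself fixes the index and the windows, and section 9.8 commits the analysis to following it strictly, so the protocol is the right place for the rule.

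**Conclusion.** The point holds as a gap in the definitions. Under the stated rules, a patient indexed on a maintenance vial is scored for step-up RAI, premedication, step-up resource use and CRS/ICANS in a window that is not an observed step-up, and nothing prevents it.

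For CRS and ICANS, events before the false index can only lower the reported percentages. The illustrative loss is 2.9 to 11.5 percentage points for an affected share of 5% to 20%, given a true rate of 57.7% and CRS before index in all affected patients. For RAI and resource use, the individual records are wrong, but the net direction for the cohort cannot be stated. The actual frequency cannot be derived from the documents and may be small. That supports counting and a sensitivity analysis, not a change to the index rule.

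**What to change.** - In section 9.7.2, flag as *step-up not observed* any patient whose index claim shows only the maintenance-size vial of Table 4 (76 mg) or Table 5 (153 mg), and report the count per cohort.
- Add a sensitivity analysis that excludes flagged patients from the denominators for step-up RAI, step-up resource use and cost, premedication, and CRS/ICANS. Keep the main analysis and the index date as defined; do not re-date index to an earlier admission.
- Report beside the flag how many index claims have an unknown or missing vial, because these cannot be classified.
- Name unobserved initial doses as a limitation in section 9.9.
- Before coding the teclistamab flag, reconcile the vial entries: Table 3 gives 153mg/7mL and Table 5 gives 153 mg/1.7mL.

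The cost is a little programming on a variable already derived, plus one sensitivity table. The price is smaller denominators in a cohort that is already small. With vial codes taken as correct, the flagged count is a lower bound, since claims with unknown or missing vial size escape it.

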9.2.2. Exclusion Criteria

Patients meeting any of the following criteria will not be included in the study:

1. Treatment with teclistamab any time prior to index date
2. For the exploratory cohort of patients receiving teclistamab, patients will be excluded based on prior use of elranatamab.

9.3. Variables

Table 1 includes definitions and assessment periods for all study variables that will be used as eligibility criteria. The full code list can be found in ANNEX 2. ADDITIONAL INFORMATION.

Table 1. Variables Used to Determine Eligibility

Variable	Operational Definition	Role	Assessment Period
Elranatamab	Prescription claim or medical claim with a National Drug Code (NDC), Healthcare Common Procedure Coding System (HCPCS), ICD-10 code or generic name in the IP, non-IP or pharmacy setting for elranatamab	Inclusion	Index event
Teclistamab	Prescription claim or medical claim with an NDC, HCPCS, ICD-10 code or generic name in the IP, non-IP or pharmacy setting for teclistamab	Exclusion	All available data to index date

Variable	Operational Definition	Role	Assessment Period
Age	Age is greater than or equal to 18 years and is not missing	Inclusion	Index date
MM diagnosis	Medical claim in the IP or non-IP setting with an ICD-10 code for MM	Inclusion	All available data to index date
Observability	Closed-claims medical and pharmacy enrollment	Inclusion	180 days prior to index date to index date (inclusive)

Table 2 includes definitions and assessment periods for all study variables that will be used as baseline and treatment characteristics. The full code list can be found in ANNEX 2.
 ADDITIONAL INFORMATION. If applicable, the frequency and percentage of patients with missing data for each variable will be described.

Table 2. Variables Used to Determine Baseline and Treatment Characteristics

Objective	Variable	Definition	Assessment Period(s)
1	Age	Age in years (continuous)	Index date
1	Sex	Categorical sex Male Female	Index date
1	Race/Ethnicity	Categorical race and ethnicity Caucasian African American Asian or Pacific Islander Hispanic or Latino Other	Start of data availability to index date

Objective	Variable	Definition	Assessment Period(s)
		Unknown	
1	Region	Categorical region, assessed as the most recent value from index date Northeast Midwest West South	Start of data to index date
	Insurance type	Categorical insurance type, assessed as the most recent value to index date Commercial Medicaid Medicare Other Unknown	180 days prior to index date to index date
1	Location (Zip code)	Categorical zip code assessed as the most recent value from index date. The full categories will be reported during implementation.	Index date
1	Care setting	Categorical care setting for elranatamab or teclistamab administration IP Non-IP Pharmacy	Index date
1	Time since MM diagnosis	Time (in months) from first MM diagnosis to index date (continuous)	MM diagnosis to index date

Objective	Variable	Definition	Assessment Period(s)
1	Triple class exposed	
Medical claim in the IP, Non-IP or pharmacy setting with an NDC, HCPCS, Current Procedural Terminology (CPT), generic name, or ICD-10 procedure code for all the following therapies in the IP, non-IP, or pharmacy setting (dichotomous)¹⁶:
 
 • ≥ 1 claim for PIs (see generic names below) • ≥ 1 claim for IMiDs (see generic names below) • ≥ 1 claim for CD38 mAbs (generic names: daratumumab, isatuximab) 	MM diagnosis to 1 day prior to index date
1	Penta-drug exposed	
Medical claims with an NDC, HCPCS, CPT, generic name, or ICD-10 procedure codes in the IP, non-IP or pharmacy setting for all of the following therapies (dichotomous)¹⁶:
 
 • ≥ 2 distinct claims for PIs (see generic names below) • ≥ 2 distinct claims for IMiDs (see generic names below) • ≥ 1 claim for CD38 mAbs (generic names: daratumumab, isatuximab) 	MM diagnosis to 1 day prior to index date
1	Hematopoietic Stem Cell Transplantation ¹	
Medical claim with an HCPCS, CPT, or ICD-10 code for hematopoietic stem cell transplantation in the IP, non-IP setting (dichotomous)
	
MM diagnosis to 1 day prior to index date
 
Index date to the end of follow-up

1	BCMA-directed therapy ¹	
Medical claim with an NDC, HCPCS CPT, generic name or ICD-10 procedure code in the IP, non-IP, or pharmacy setting for idecabtagene vicleucel, ciltacabtagene autoleucel, or belantamab (dichotomous)
	
MM diagnosis to 1 day prior to index date
 
Index date to the end of follow-up

1	CAR-T ¹	
Medical claim with an NDC, HCPCS, generic name or CPT code in the IP, non-IP, or pharmacy setting for idecabtagene vicleucel or
	
MM diagnosis to 1 day prior to index date

Objective	Variable	Definition	Assessment Period(s)
		ciltacabtagene autoleucel (dichotomous)	Index date to the end of follow-up
1	Talquetamab ¹	Medical claim with an NDC, HCPCS, generic name or CPT code in the IP, non-IP, or pharmacy setting for talquetamab (dichotomous)	MM diagnosis to 1 day prior to index date Index date to the end of follow-up
1	PIs ¹	Medical claim with an NDC, HCPCS, generic name or CPT code in the IP, non-IP, or pharmacy setting for bortezomib, carfilzomib, or ixazomib (dichotomous)	MM diagnosis to 1 day prior to index date Index date to the end of follow-up
1	IMiDs ¹	Medical claim with an NDC code or generic name in the non-IP or pharmacy setting for lenalidomide, thalidomide, or pomalidomide (dichotomous)	MM diagnosis to 1 day prior to index date Index date to the end of follow-up
1	Steroids ¹	Medical claim with an NDC, HCPCS, generic name or CPT code in the IP, non-IP, or pharmacy setting for dexamethasone, methylprednisolone, prednisone, or prednisolone (dichotomous)	MM diagnosis to 1 day prior to index date Index date to the end of follow-up
1	MAbs ¹	Medical claim with an NDC, HCPCS, generic name or CPT code in the IP, non-IP, or pharmacy setting for daratumumab, isatuximab, or elotuzumab (dichotomous)	MM diagnosis to 1 day prior to index date Index date to the end of follow-up
1	Chemotherapies ¹	Medical claim with an NDC, HCPCS, generic name or CPT code in the IP, non-IP, or pharmacy setting for	MM diagnosis to 1 day prior to index date

Objective	Variable	Definition	Assessment Period(s)
		doxorubicin hydrochloride, melphalan, bendamustine, cyclophosphamide, etoposide, or cisplatin (dichotomous)	Index date to the end of follow-up
1	Small molecule inhibitors ¹	Medical claim with an NDC, HCPCS, generic name or CPT code in the IP, non-IP, or pharmacy setting for venetoclax (dichotomous)	MM diagnosis to 1 day before index date Index date to the end of follow-up
1	Nuclear export inhibitors ¹	Medical claim with an NDC, HCPCS, generic name or CPT code in the IP, non-IP, or pharmacy setting for selinexor (dichotomous)	MM diagnosis to 1 day before index date Index date to the end of follow-up
1	Antivirals ¹	Medical claim with an NDC, HCPCS, generic name or CPT code in the IP, non-IP, or pharmacy setting for antiviral medications (dichotomous)	14 days prior to index date to 1 day prior to index date Index date to the end of follow-up
1	Antibiotics ¹	Medical claim with an NDC, HCPCS, generic name or CPT code in the IP, non-IP, or pharmacy setting for antibiotic medications (dichotomous)	14 days prior to index date to 1 day prior to index date Index date to the end of follow-up
1	Antifungal Medication ¹	Medical claim with an NDC, HCPCS, generic name or CPT code in the IP, non-IP, or pharmacy setting for antifungal medications (dichotomous)	14 days prior to index date to 1 day prior to index date Index date to the end of follow-up
1	Intravenous immunoglobulin ¹	Medical claim with an NDC, HCPCS, generic name, CPT, or ICD-10 procedure code in the IP, non-IP, or pharmacy setting for intravenous	14 days prior index date to 1 day prior to index date

Objective	Variable	Definition	Assessment Period(s)
		immunoglobulin administration (dichotomous)	Index date to the end of follow-up
1	Other hematological malignancies	Medical claim with an ICD-10 code in the IP or non-IP setting for hematological malignancies other than MM (dichotomous)	MM diagnosis to 1 day prior to index date
1	Any non-hematological malignancy	Medical claim with an ICD-10 code in the IP or non-IP setting for non-hematological malignancies (dichotomous)	MM diagnosis to 1 day prior to index date
1	Plasma cell leukemia	Medical claim with an ICD-10 code in the IP or non-IP setting for plasma cell leukemia (dichotomous)	MM diagnosis to 1 day prior to index date
1	Bone lesions	Medical claim with an ICD-10 code in the IP or non-IP setting for bone lesions (dichotomous)	MM diagnosis to 1 day prior to index date
1	Peripheral neuropathy	Medical claim with an ICD-10 code in the IP or non-IP setting for peripheral neuropathy (dichotomous)	MM diagnosis to 1 day prior to index date
1	Any infection	Medical claim with an ICD-10 code in the IP or non-IP setting for any infection of the following types (dichotomous): COVID-19 Sinusitis Bronchitis Adenoviral pneumonia Cytomegaloviral pneumonitis Other Pneumonia Upper respiratory tract infection	MM diagnosis to 1 day prior to index date

Objective	Variable	Definition	Assessment Period(s)
		
Sepsis
 
Cytomegaloviral infection
 
Pneumocystis jiroveci pneumonia (PJP)
 
Hepatitis C
 
Hepatitis B
 
Other infectious hepatitis
 
Helicobacter pylori
 
Candida esophagitis
 
Urinary tract infection
	
1	Use of intravenous anti-infective	Medical claim with an NDC code generic name, CPT, or HCPCS code in the IP, non-IP, or pharmacy setting for anti-infective where the route of administration is intravenous for an intravenous anti-infective (dichotomous)	MM diagnosis to 1 day prior to index date
1	Neutropenia	Medical claim with an ICD-10 code in the IP or non-IP setting for neutropenia (dichotomous) or event in the lab table where absolute neutrophil count is < 1,500 cells per μ L	MM diagnosis to 1 day prior to index date
1	Hypercalcemia	Medical claim with an ICD-10 code in the IP or non-IP setting for hypercalcemia (dichotomous) or an event in the lab table where corrected serum calcium is > 11.5 mg/dL	MM diagnosis to 1 day prior to index date
1	Hepatotoxicity	Medical claim with an ICD-10 code in the IP or non-IP setting for hepatotoxicity (dichotomous)	MM diagnosis to 1 day prior to index date

Objective	Variable	Definition	Assessment Period(s)
1	Renal failure	Medical claim with an ICD-10 code in the IP or non-IP setting for renal failure (dichotomous)	MM diagnosis to 1 day prior to index date
1	Amyloidosis	Medical claim with an ICD-10 code in the IP or non-IP setting for amyloidosis (dichotomous)	MM diagnosis to 1 day prior to index date
1	Hypertension	Medical claim with an ICD-10 code in the IP or non-IP setting for hypertension (dichotomous)	MM diagnosis to 1 day prior to index date
1	Extramedullary disease	Medical claim with an ICD-10 code in the IP or non-IP setting for extramedullary disease (dichotomous)	MM diagnosis to 1 day prior to index date
1	CCI score	CCI ¹⁷ (continuous and categorical): 0 (no comorbidities) 1 to 2 (mild) 3 to 4 (moderate) ≥ 5 (severe)	180 days prior to index date to index date
1	Myocardial infarction	Medical claim with an ICD-10 code in the IP or non-IP setting for myocardial infarction (dichotomous)	180 days prior to index date to index date
1	Congestive heart failure	Medical claim with an ICD-10 code in the IP or non-IP setting for congestive heart failure (dichotomous)	180 days prior to index date to index date
1	Peripheral vascular disease	Medical claim with an ICD-10 code in the IP or non-IP setting for peripheral vascular disease (dichotomous)	180 days prior to index date to index date
1	Cerebrovascular disease	Medical claim with an ICD-10 code in the IP or non-IP setting for cerebrovascular disease (dichotomous)	180 days prior to index date to index date

Objective	Variable	Definition	Assessment Period(s)
1	Dementia	Medical claim with an ICD-10 code in the IP or non-IP setting for dementia (dichotomous)	180 days prior to index date to index date
1	Chronic pulmonary disease	Medical claim with an ICD-10 code in the IP or non-IP setting for chronic pulmonary disease (dichotomous)	180 days prior to index date to index date
1	Rheumatic disease	Medical claim with an ICD-10 code in the IP or non-IP setting for rheumatic disease (dichotomous)	180 days prior to index date to index date
1	Peptic ulcer disease	Medical claim with an ICD-10 code in the IP or non-IP setting for peptic ulcer disease (dichotomous)	180 days prior to index date to index date
1	Liver disease	Medical claim with an ICD-10 code in the IP or non-IP setting for liver disease (dichotomous)	180 days prior to index date to index date
1	Diabetes	Medical claim with an ICD-10 code in the IP or non-IP setting for diabetes (dichotomous)	180 days prior to index date to index date
1	Renal disease	Medical claim with an ICD-10 code in the IP or non-IP setting for renal disease (dichotomous)	180 days prior to index date to index date
1	Hemiplegia or paraplegia	Medical claim with an ICD-10 code in the IP or non-IP setting for hemiplegia or paraplegia (dichotomous)	180 days prior to index date to index date
1	Human immunodeficiency virus	Medical claim with an ICD-10 code in the IP or non-IP setting for human immunodeficiency virus (dichotomous)	180 days prior to index date to index date
1	Metastatic solid tumor	Medical claim with an ICD-10 code in the IP or non-IP setting for metastatic solid tumor (dichotomous)	180 days prior to index date to index date

Objective	Variable	Definition	Assessment Period(s)
1	Albumin serum	Lab event with albumin serum as the test name and g/dL as the result units (dichotomous)	180 days prior to index date to index date
		Most recent numeric value to index date of a lab event with albumin serum as the test name and g/dL as the result units (continuous)	
1	Alanine aminotransferase (ALT)	Lab event with ALT as the test name and IU/L as the result units (dichotomous)	180 days prior to index date to index date
		Most recent numeric value to index date of a lab event with ALT as the test name and IU/L as the result units (continuous)	
1	Aspartate aminotransferase (AST)	Lab event with AST as the test name and IU/L as the result units (dichotomous)	180 days prior to index date to index date
		Most recent numeric value to index date of a lab event with AST as the test name and IU/L as the result units (continuous)	
1	Neutrophil count	Lab event with neutrophil as the test name and thousands/ μ L as the result units (dichotomous)	180 days prior to index date to index date
		Most recent numeric value to index date of a lab event with neutrophil count as the test name and thousands/ μ L result units (continuous)	
1	Creatinine	Lab event with creatinine as the test name and mg/dL as the result units (dichotomous)	180 days prior to index date to index date

Objective	Variable	Definition	Assessment Period(s)
		Most recent numeric value of a lab event to index date with creatinine as the test name and mg/dL as the result units (continuous)	
1	Hemoglobin	Lab event with hemoglobin as the test name and g/dL as the result units (dichotomous)	180 days prior to index date to index date
		Most recent numeric value of a lab event with hemoglobin as the test name and g/dL as the result units (continuous)	
1	Lymphocyte count	Lab event with lymphocyte count as the test name and thousand/ μ L as the result units (dichotomous)	180 days prior to index date to index date
		Most recent numeric value of a lab event with lymphocyte count as the test name and thousand/ μ L as the result units (continuous)	
1	Monocyte count	Lab event with monocyte count as the test name and thousand/ μ L as the result units (dichotomous)	180 days prior to index date to index date
		Most recent numeric value of a lab event with monocyte count as the test name and thousand/ μ L as the result units (continuous)	
1	Platelet Count	Lab event with platelet count as the test name and thousand/ μ L as the result units (dichotomous)	180 days prior to index date to index date
		Most recent numeric value of a lab event with platelet count as the test name and thousand/ μ L as the result units (continuous)	

Objective	Variable	Definition	Assessment Period(s)
1	Serum immunoglobulin A (IgA)	Lab event with IGA as the test name and mg/dL as the result units (dichotomous)	180 days prior to index date to index date
		Most recent numeric value of a lab event with IGA as the test name and mg/dL as the result units (continuous)	
1	Serum immunoglobulin G (IgG)	Lab event with IGG as the test name and mg/dL as the result units (dichotomous)	180 days prior to index date to index date
		Most recent numeric value of a lab event with IGG as the test name and mg/dL as the result units (continuous)	
1	Serum immunoglobulin E (IgE)	Lab event with IGE as the test name and IU/mL as the result units (dichotomous)	180 days prior to index date to index date
		Most recent numeric value of a lab event with IGE as the test name and IU/mL as the result units (continuous)	
1	Serum immunoglobulin M (IgM)	Lab event with IGM as the test name and mg/dL as the result units (dichotomous)	180 days prior to index date to index date
		Most recent numeric value of a lab event with IGM as the test name and mg/dL as the result units (continuous)	
1	Bone marrow plasma cell percent	Lab event with bone marrow plasma cell percent as the test name and percent as the result units (dichotomous)	Most recent value recorded in the 180 days prior to index date to index date
		Most recent numeric value of a lab event with bone marrow plasma cell	

Objective	Variable	Definition	Assessment Period(s)
		percent as the test name and percent as the result units (continuous)	
1	M-Protein	Lab event with M-Spike as the test name and as the g/dL as the result units (dichotomous)	180 days prior to index date to index date
		Most recent numeric value of a lab event with M-Spike as the test name and g/dL as the result units (continuous)	

1. Variable assessed both at baseline and in follow-up

Table 3 includes definitions and assessment periods for all study variables being used as outcomes. The full code list can be found in ANNEX 2. ADDITIONAL INFORMATION. If applicable, the frequency and percentage of patients with missing data for each variable will be described.

Table 3. Key Variables of Interest

Objective	Variable	Definition	Assessment Period(s)
Treatment exposure			
2	Use of premedication	
Medical or pharmacy claim with evidence of an NDC, HCPCS, generic name or CPT code for the following premedications (dichotomous):
 
Acetaminophen
 
Dexamethasone
 
Diphenhydramine
	
Step-Up Dosing Period
 
See Section 9.7.2 for censoring criteria

